7.3 Central Pathology Evaluation

All efficacy endpoints assessment will be based on central pathology consensus panel results to reduce the difference between the pathological evaluations used in the efficacy analysis.

The WHO 2016 World Health Organization/International Society of Urologic Pathology consensus classification and the Union for International Cancer Prevention (UICC) 2017 8th edition of TNM classification for staging of bladder cancer will be used to grade and stage tumors. Two independent pathologists unaware of the diagnosis of the local pathologist and whether the biopsy came from a lesion seen in white light or blue light or both, provide a pathology diagnosis independently. If the two pathologists agree on the diagnosis, this is the final diagnosis. If they disagree, a third independent pathologist will make a diagnosis without knowing the diagnosis of the two first pathologists. If this diagnosis is in agreement with the diagnosis made by the one of the first pathologists, this result will be the final diagnosis. If they agree on a diagnosis, this will be the final consensus diagnosis. If they fail to reach agreement, this lesion will be excluded from the statistical analysis.

A histologically confirmed malignancy is a tumor staged/graded as CIS, Ta, T1 orT2-T 4 by the consensus panel. Lesions can be classified to PUNLMP, low grade and high grade.

7.4 Efficacy Parameters

Efficacy parameters recorded in eCRF will be used in both analyses of the primary and secondary endpoints.

7.4.1 Detection of Lesions by White Light Cystoscopy

Number of lesions and suspicious areas seen.

Study Number: YHCT-HEX-B1

- Type of lesion and suspicious area seen (flat or papillary).
- Location of lesions and suspicious areas (Bladder neck anterior, trigone, around ureteric orifice right, around ureteric orifice left, posterior floor, right lateral wall, cranial wall, left lateral wall, dome, anterior bladder wall, bladder neck posterior).

7.4.2 Detection of Lesions by Blue Light Cystoscopy

- Number of fluorescent lesions and suspicious areas seen.
- Type of fluorescence lesions and suspicious areas seen (flat or papillary).
- Location of fluorescent lesions and suspicious areas (Bladder neck anterior, trigone, around ureteric orifice right, around ureteric orifice left, posterior floor, right lateral wall, cranial wall, left lateral wall, dome, anterior bladder wall, bladder neck posterior)

7.4.3 Subject Diagnosis

Subject diagnosis will be recorded including the assessments performed. This will include the staging and grading based on the use of cystoscopy, biopsies/histology, cytology, markers and/or other test(s).

Study Number: YHCT-HEX-B1

8. Assessment of Safety

8.1 Adverse Events

8.1.1 Definition Adverse Event

An adverse event is defined as any untoward medical occurrence in a patient from signing the ICF to the completion of the last visit specified in the flowchart (visit 3) and which does not necessarily have to have a causal relationship with this treatment.

An adverse event can therefore be any unfavourable and unintended sign (including an abnormal laboratory finding), symptom, or disease temporally associated with the use of a medicinal product, whether or not related to the medicinal product.

Symptoms/signs that begin or worsen in severity and/or frequency after Hexvix instillation will be recorded as AEs in the eCRF.

Examples of adverse events may include the following factors:

- A new sign, symptom, illness, or syndrome
- Worsening of a concomitant disease, sign or symptom at baseline
- An effect of investigational product, including comparator or concomitant medication
- An effect of an invasive procedure required by the protocol
- An accident or injury

Surgical procedures themselves are not adverse events; they are therapeutic measures for conditions that require surgery. The condition for which the surgery is required is an adverse event, if it occurs or is detected after the administration of Hexvix. Planned surgical measures permitted by the clinical study protocol, i.e., surgical treatment for bladder cancer, are not adverse events.

8.1.2 Period of Observation

The period of observation is defined as the period from instillation of Hexvix until the end of the study.

8.1.3 Reporting of Adverse Events

All adverse events occurring during the period of screen and observation must be documented on the adverse event form in the eCRF.

A baseline recording of clinical bladder cancer symptoms will be performed before administration of Hexvix. Only symptoms that increase in severity or new symptoms of any illness will be recorded as adverse events in the eCRF.

Every attempt should be made to describe the adverse event in terms of a diagnosis. If a clear diagnosis has been made, individual signs and symptoms will not be recorded unless they represent atypical or extreme manifestations of the diagnosis. For example, if myocardial infarction is reported as an AE, there is no need to report elevated creatine phosphokinase and abnormal ECG, or other related signs, symptoms, or laboratory values as separate AEs. However, if both occurred in isolation and myocardial

Study Number: YHCT-HEX-B1

infarction was not diagnosed, then each event would be reported as an AE. In this case they should be reported as separate events. If a clear diagnosis cannot be established, each sign and symptom must be recorded individually.

AEs will be recorded as follows:

- All AEs occurring in the period of observation, whether or not considered related to Hexvix and/or blue light, will be recorded
- All SAEs that are considered related to Hexvix and/or blue light occurring after the period of observation, but before database lock, will be recorded in the eCRF and included in the clinical database

All SAEs that are considered related to Hexvix and/or blue light occurring after database lock will be reported to the sponsor and included in the safety database only. The sponsor will code all adverse events according to current standard dictionary (MedDRA).

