	• The lesion detection rate for Hexvix blue light cystoscopy compared to white light cystoscopy per lesion type (PUNLMP, CIS, Ta, T1, T2-4).
	The proportion of false positive lesions detected with Hexvix blue light cystoscopy and white light cystoscopy.
Safety Endpoint	The proportion of patients with AEs during the study.

Sample Size:

Sample size calculation for the primary efficacy analysis is based on an exact test for a single proportion. Statistical assumption is based on primary endpoint that P (null hypothesis) is 10%, P (alternative hypothesis) is 20% and a power of 80%, α (1-side) is 0.025, a total of 94 patients with histologically confirmed Ta, T1, and CIS stage bladder cancer are needed.

Assuming that 35% of subjects will have bladder cancer after Hexvix-assisted blue light cystoscopy and/or white light cystoscopy, bladder cancer with Ta, T1 and CIS stage accounting for 75%, 359 subjects are expected to be enrolled in this trial. Considering the 5% drop-out rate, a total of about 380 subjects are required. The study will continue until 94 subjects have bladder cancer after Hexvix-assisted blue light cystoscopy and/or white light cystoscopy and are pathologically confirmed as Ta, T1, and CIS stage bladder cancer.

Note: A minimum of 4 subjects included at each center will be training subjects, and those training subjects are in addition to the estimated sample size. Moreover, training subjects are not included in the randomization procedure and efficacy endpoints analysis, but included in the safety analysis.

Statistical Analysis Method:

Efficacy:

Statistics

Efficacy endpoint analysis will be based on full analysis set (FAS) / modified full analysis set (mFAS) and per protocol set (PPS) / modified per protocol set (mPPS). Primary efficacy endpoint will be analyzed based on subjects who received Hexvix instillation and continue with blue light cystoscopy, and are pathologically confirmed as Ta, T1, and CIS stage bladder cancer, training patients will not be included.

For analysis of the primary efficacy endpoint (The proportion of patients with histology-confirmed tumors (Ta, T1, or CIS) who have at least one such tumor found by Hexvix but not by white light cystoscopy), an exact test for single proportion, using the cumulative binominal distribution, with a significance level of 0.025 (1-sided) will be used, based on the mFAS and mPPS, and the 95% confidence interval for the detection rate will be calculated.

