8.1.4 Severity of Adverse Events

The intensity of all AEs will be graded as mild, moderate, or severe using the following definitions:

Mild	the adverse event is transient and easily tolerated
Moderate	the adverse event causes the patient discomfort and interrupts the
	patient's usual activities
Severe	the adverse event causes considerable interference with the patient's
	usual activities and may be incapacitating or life-threatening

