10.3 Statistical Analysis Populations

10.3.1 Safety Set

All subjects who receive Hexvix instillation will be included in the safety population (including training subjects for investigators).

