10.4.3.1 Adverse Event

Adverse event will be coded according to MedDRA terminology, using descriptive statistics and annlysis by System Organ Class and by Preferred term.

The overall incidence of adverse events, adverse reactions, treatment-emergent adverse events, study drug-related adverse events, significant adverse events, serious adverse events, and the incidence by SOC/PT will be calculated. The number and number of patients with treatment-emergent adverse events, adverse events will be summarized by SOC and severity. Adverse events, adverse reactions, treatment-emergent adverse events, adverse events related to the study drug, significant adverse events and serious adverse events should be listed in detail.

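### Sections 8.1.1 and 8.1.3 give conflicting eCRF recording rules for a baseline symptom that becomes more frequent, but not more severe, after Hexvix instillation

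*Combined protocol and SAP*

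**What the plan says.** Two sentences in the protocol govern the same act, entering a symptom as an adverse event in the eCRF.

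- Section 8.1.1: "Symptoms/signs that begin or worsen in severity and/or frequency after Hexvix instillation will be recorded as AEs in the eCRF". Its list of examples includes "Worsening of a concomitant disease, sign or symptom at baseline", with no limit to severity.
- Section 8.1.3: "A baseline recording of clinical bladder cancer symptoms will be performed before administration of Hexvix". The next sentence reads: "Only symptoms that increase in severity or new symptoms of any illness will be recorded as adverse events in the eCRF".

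Section 8.1.4 defines severity: "The intensity of all AEs will be graded as mild, moderate, or severe using the following definitions". Those definitions rest on how well the event is tolerated and how far it disturbs usual activities. Frequency is not a criterion.

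The synopsis gives the safety endpoint as "The proportion of patients with AEs during the study". Section 10.4.3.1 builds further summaries on the same records: "significant adverse events, serious adverse events, and the incidence by SOC/PT will be calculated". The denominator is set in Section 10.3.1: "All subjects who receive Hexvix instillation will be included in the safety population (including training subjects for investigators").

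**The concern.** Section 8.1.1 joins severity and frequency with and/or, so a rise in frequency is enough on its own. The sentence in 8.1.3 is restrictive and leaves frequency out. Two sites could each follow a sentence of the approved protocol and reach opposite entries for the same patient, and neither would show up as a protocol deviation.

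Bladder symptoms are where this matters most. They are what the protocol has sites record before instillation, and the product is instilled into the bladder through a catheter, followed by cystoscopy and resection or biopsy. The safety analysis expressly includes local reactions (Section 10.4.3). At stake is whether the adverse event counts, the incidences by system organ class and preferred term, and the safety endpoint have one operational definition across the planned 5 to 10 centers. An event that was never entered cannot be restored at the analysis stage. Visit 3 may be a telephone contact (Section 4.3.3), so detail not collected at the time may be hard to recover.

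**Working it through.** The plan attaches no figure to this point, so there is none to reproduce. The check compares the two rules, looks for text that reconciles them, and then works out how much one patient weighs in the endpoint.

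**Step 1. The rules side by side.**

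| Symptom after instillation, compared with baseline | 8.1.1 | Restrictive sentence in 8.1.3 |
|---|---|---|
| New | recorded | recorded |
| Present at baseline, more severe | recorded | recorded |
| Present at baseline, more frequent and more severe | recorded | recorded |
| Present at baseline, more frequent, same severity | recorded | not recorded |
| Present at baseline, unchanged | not recorded | not recorded |

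The rules differ in one row only. The direction is fixed: the 8.1.3 sentence can only give the same number of events as 8.1.1 or fewer.

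**Step 2. Does other text reconcile them?**

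- Section 8.1.4: a rise in frequency that disturbs activities more may move the event up a grade and so satisfy both rules. A rise that does not change the grade stays in the disputed row.
- Study Flow Chart, note 8: worsened events are to be recorded, but the note does not say whether frequency counts as worsening.
- Sections 10.4.3 and 10.4.3.1: these say how recorded events are tabulated, not which ones are entered.

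None of these decides the disputed row.

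**Step 3. Weight of one patient in the safety endpoint.**

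Inputs: about 380 subjects, with at least 4 training subjects per center in addition (Section 10.2); about 5 to 10 centers (synopsis); training subjects belong to the safety set (Section 10.3.1).

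- Training subjects: 5 × 4 = 20 to 10 × 4 = 40.
- Safety set: 380 + 20 = 400 to 380 + 40 = 420. This treats every enrolled subject as instilled and uses the minimum number of training subjects, so it is approximate.
- One patient changing status: 100/400 = 0.25 to 100/420 = 0.24 percentage points.

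A patient changes status only if the frequency-only worsening is the sole recorded adverse event. A patient with any other recorded event counts in the numerator under both rules, although that patient's event count, and possibly a preferred-term incidence, still differs.

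**Step 4. Scale, by assumption only.** The documents give no rate for patients whose only event is of this kind. If that share of the safety set were:

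- 1%: 0.01 × 400 to 420 = about 4 patients, 1 point on the endpoint
- 2%: about 8 patients, 2 points
- 5%: 20 to 21 patients, 5 points
- 10%: 40 to 42 patients, 10 points

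These lines convert a share into patients. They are not a forecast.

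**The case against.** The strongest reply is that the 8.1.3 sentence was never meant to redefine an adverse event. It directly follows the baseline recording of bladder cancer symptoms, and its evident purpose is to keep unchanged baseline complaints out of the adverse event form. Section 8.1.3 itself opens by requiring that all adverse events be documented and repeats this for the observation period. Note 8 of the flow chart asks for all events whatever their severity. Most of the text therefore favors inclusion, and many sites may record frequency-only worsening anyway. The affected class is also narrow, safety is summarized descriptively with no hypothesis test or threshold, and the primary efficacy analysis is untouched.

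Much of this stands. It limits the consequence and makes it wrong to say that events will be lost at every site. It does not remove the conflict. Section 8.1.1 states no exception, and the 8.1.3 sentence does not present itself as one, since it extends to new symptoms of any illness. Even if it is read as a special rule for bladder symptoms, the two sections still disagree for those symptoms.

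A reader might go further and infer that local reactions will be understated by a material amount. For example, if 30 to 50% of subjects had a baseline bladder symptom and 10 to 20% of those had only a rise in frequency, then 380 × 0.30 × 0.10 = 11 to 380 × 0.50 × 0.20 = 38 patients would switch between having and not having an adverse event. The documents do not support that. Neither pair of percentages appears in them, 380 is not the full safety set, and the count ignores that patients with another recorded event do not switch. On its own assumptions it is a ceiling.

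**Conclusion.** The two sections conflict, in the current text, for one class of event: a symptom present at baseline that becomes more frequent without becoming more severe after instillation. Where a site applies the 8.1.3 sentence literally, fewer such events are entered than under 8.1.1, and event counts and incidences by system organ class and preferred term are lower. The safety endpoint moves by about 0.24 to 0.25 percentage points for each patient who has no other recorded adverse event. That figure rests on a safety set of about 400 to 420.

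The total effect cannot be estimated, because the documents give neither the frequency of such events nor the rule that sites will follow. The conflict itself is certain; understatement is conditional on site practice. The point deserves correction because it leaves the listed safety endpoint without a single recording rule. It does not bear on the primary endpoint.

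**What to change.** Reconcile the sections by replacing the restrictive sentence in 8.1.3 with wording that matches 8.1.1: record new symptoms, and baseline symptoms that worsen in severity and/or frequency. Draft it so that it does not narrow adverse event collection, which runs from signature of the consent form. The pre-instillation assessment should not turn a symptom that began or worsened between consent and instillation into an unreported baseline finding.

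Also confirm that the bladder symptom assessment already scheduled before instillation at Visit 2 (Section 4.3.2) records frequency as well as severity. The form is not shown in the documents, so whether a field needs to be added is unknown.

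The cost is one sentence, a check of an existing form, and possibly one field. The reported adverse event rate may be slightly higher.

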8.1.4 Severity of Adverse Events

The intensity of all AEs will be graded as mild, moderate, or severe using the following definitions:

Mild	the adverse event is transient and easily tolerated
Moderate	the adverse event causes the patient discomfort and interrupts the
	patient's usual activities
Severe	the adverse event causes considerable interference with the patient's
	usual activities and may be incapacitating or life-threatening

8.1.5 Relationship of Adverse Event to the Drug

The causality assessment of adverse events will be done by the performing clinical investigator urologist. Relationship to Hexvix and/or blue light will be categorized as "yes" or "no" or "uncertain", of which the "yes" and "uncertain" are considered as Adverse Drug Reaction (ADR):

Yes	an adverse event which after careful examination at the time of evaluation,
	appears to be related to Hexvix and/or blue light
No	an adverse event which after careful examination at the time of evaluation, is judged to be clearly and incontrovertibly due to extraneous causes (disease, environment, etc) and do not meet the criteria described under "yes"
Uncertain	there is no clear relevance between the event and the time of administration, the event is similar to the known reaction type of the investigational drug, while the same reaction may be caused due to the use of other drugs. Therefore, there is no sufficient basis for the determination.

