Two small single center studies reported improved detection of bladder cancer lesions using blue light cystoscopy with Hexvix [18, 19], and another small single center study documented the use of Hexvix in the early follow up of high-risk patients [20]. The studies were conducted in the OR setting, and concluded that blue light cystoscopy with Hexvix helps to detect evolving CIS and dysplasia which can be considered a precursor of CIS, and plays an important role in preventing disease progression.

The safety of Hexvix instillation into the bladder has been evaluated in all clinical trials, and similar AE profiles have been reported for patients undergoing blue light cystoscopy with Hexvix versus patients treated with white light cystoscopy only [15]. Most AEs were mild to moderate and were expected during bladder examination by cystoscopy, and were considered to be related to general anesthesia, biopsy, tumor resection, cystoscopy or the patients' underlying disease. The conclusions were that Hexvix is well tolerated. A review of safety information from clinical studies and postmarketing data did not reveal additional toxicity during repeated use of Hexvix [21].

The trial is a phase III, prospective, comparative, within patient controlled, multi-center study of Hexvix blue light cystoscopy and white light cystoscopy in the detection of bladder cancer and will be conducted only in China to evaluate the efficacy and safety of Hexvix blue light cystoscopy in Chinese population.

Study Number: YHCT-HEX-B1

2. Study Objectives

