10.4.3 Safety Analysis

Safety analysis will be based on safety set.

The reported adverse events (including local reactions) will be coded according to MedDRA terminology. The events will be tabulated by System Organ Class and by Preferred term.

Adverse events will also be tabulated versus severity and relation to treatment.

Study Number: YHCT-HEX-B1

Physical examination and vital signs at each visit will be presented using descriptive statistics.

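### The causality item in section 8.1.5 merges Hexvix with blue light, records no procedure attribution and has no clean category for same-day events, so the ADR rate depends on site coding and is not specific to Hexvix

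*Combined protocol and SAP*

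**What the plan says.** Section 8.1.5 has the operating urologist answer a single item: "Relationship to Hexvix and/or blue light will be categorized as" yes, no or uncertain. Both 'Yes' and 'Uncertain' "are considered as Adverse Drug Reaction (ADR").

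- 'Yes': after careful examination, the event appears related to Hexvix and/or blue light.
- 'No': the event "is judged to be clearly and incontrovertibly due to extraneous causes". Disease and environment are the examples, and the list is left open.
- 'Uncertain' has three conditions. The first two are that "there is no clear relevance between the event and the time of administration, the event is similar to the known reaction type" seen with Hexvix; the third is that other drugs could have produced the same reaction. The definition concludes that there is no sufficient basis to decide.

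Section 8.1.1 counts effects of a protocol-required invasive procedure as AEs. Section 1.2.2 reports that most AEs in earlier trials were expected with cystoscopy and "were considered to be related to general anesthesia, biopsy, tumor resection, cystoscopy" or the underlying disease.

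On analysis, section 10.3.1 says: "All subjects who receive Hexvix instillation will be included in the safety population (including training subjects for investigators"). Section 10.4.3 says: "The events will be tabulated by System Organ Class and by Preferred term", and adds tables by severity and relation to treatment. Section 10.4.3.1 lists 'adverse reactions' and 'study drug-related adverse events' as separate summaries without saying how they differ. The synopsis defines the safety endpoint as the proportion of patients with AEs.

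**The concern.** Every subject receives Hexvix, a catheter and cystoscopy on the same day, and those with lesions also have biopsy or resection. Events such as dysuria, haematuria or bladder spasm that evening have at least two candidate causes, and most randomized subjects also have blue light as a third. The scale asks about two of these causes in one question and does not ask about the procedure, which section 1.2.2 puts among the main sources of AEs in earlier trials.

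Evaluating the safety of Hexvix is a secondary objective. If the field behind the ADR tables cannot distinguish drug, light and procedure, those tables mix the three in proportions set by local coding habits. Attribution that was never collected cannot be recovered later by an analysis plan.

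**Working it through.** **1. Applying the categories.** Take dysuria that starts a few hours after instillation and TURBT, where the investigator cannot tell which caused it.

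| Category | What 8.1.5 requires | Does the event meet it? |
|---|---|---|
| Yes | Appears related to Hexvix and/or blue light | Not on this evidence; the investigator cannot tell |
| No | Extraneous cause, clear and incontrovertible | The procedure may count as extraneous, but the standard is hard to meet when drug and procedure share a day |
| Uncertain | No clear time relation; resembles a known drug reaction; other drugs as rival cause | Timing condition fails; the rival cause is a procedure, not a drug |

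No row fits cleanly. Two careful sites could code the same event differently, and two of the three codes make it an ADR.

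**2. What depends on this field.**

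- Section 10.4.3.1 promises drug-related AEs. The field yields only events related to Hexvix, blue light or both.
- The heading of section 10.4.3.3 includes device events, but section 8.1.5 does not record relatedness to blue light on its own.
- Late SAE collection refers to Hexvix and/or blue light in section 8.1.3, to the study intervention in 8.2.2 and to the investigational drug in 8.3.2. One field serves three different objects.
- Section 8.1.6 follows related events until resolution, so the code also determines follow-up.

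**3. Sensitivity to coding (illustration only).** The documents give no AE or ADR rate, so there is no plan figure to reproduce. Let t be the share of patients with a true reaction, b the share with a procedure event (taken as independent of t), and u the share of procedure events coded other than 'No'. Then ADR rate = t + (1 − t) × b × u. All inputs are assumed.

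| t, b | u = 0 | u = 25% | u = 50% | u = 100% |
|---|---|---|---|---|
| 2%, 20% | 2.0% | 6.9% | 11.8% | 21.6% |
| 5%, 40% | 5.0% | 14.5% | 24.0% | 43.0% |

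For example, 0.05 + 0.95 × 0.40 × 0.50 = 0.24. Within each row only u changes, and the plan does not control u. If sites code every procedure event 'No', there is no inflation.

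**4. What the randomized groups could add.** A small, unstated number of subjects receive Hexvix and white light only. Assume they are 5% or 10% of 380, that is 19 against 361 or 38 against 342, with a common AE rate p of 20% or 40%. The 95% half-width of the difference is 1.96 × √[p(1 − p)(1/n₁ + 1/n₂)].

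| n₁ / n₂ | p = 20% | p = 40% |
|---|---|---|
| 19 / 361 | 18.5 points | 22.6 points |
| 38 / 342 | 13.4 points | 16.4 points |

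Both groups receive Hexvix, so the contrast informs only on blue light and the added resection. It is imprecise, but section 10.4.3 states no safety summary by allocation at all, whereas section 10.3.2.1 gives the white-light-only subjects their own efficacy table.

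**The case against.** A reader might infer that ordinary post-TURBT events default to ADR through 'Uncertain', or end up as ADRs whichever box is used. The documents do not support that. Read literally, a same-day event fails the timing condition of 'Uncertain'. 'Yes' needs a positive judgement and is not a residual box. The open list under 'No' lets a urologist code a clearly procedural event there. This answers the claim of automatic inflation, but it leaves the event that could be either without a home.

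It can also be said that 'Uncertain' ends by stating that the basis for a decision is insufficient, so sites will use it for doubtful cases anyway. Some will. But that sentence is drawn as a conclusion from the preceding conditions, and sites that read those conditions will not use it.

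Judging drug and light together is defensible. The European indication quoted in section 1.2 is for Hexvix blue light cystoscopy, and section 5.2 expects no complications from the light. That supports a combined summary, but separate recording would still allow one.

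The strict 'No' rule is deliberately cautious, and over-reporting is the safer error. This stands, and the threshold should be left alone.

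Finally, randomization was introduced to reduce bias in the white-light examination, not to compare safety, and section 10.1 defers analysis detail to a statistical analysis plan. Both points are fair. Tables by allocation are therefore a modest addition, and such a plan could supply them. It could not supply the missing attribution.

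**Conclusion.** The point holds as a defect in data collection and definitions. The ADR rate will depend on site coding, may be inflated by procedure events, and describes Hexvix plus blue light rather than Hexvix. The drug-related summary in section 10.4.3.1 cannot be separated from light-related or procedure-related events.

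It would be going too far to conclude that the trial cannot describe Hexvix safety. The safety endpoint is any AE and does not use the causality field. Events are also tabulated by system organ class, preferred term, severity and relation to treatment. Under section 8.2.2, SAEs in the observation period are reported whether or not they are related.

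The size of the distortion cannot be stated because the documents give no AE rate. The ADR rates and half-widths above rest on assumed inputs and show direction and sensitivity only. The change is worth making because it is cheap and has to be in place when events are recorded.

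**What to change.** 1. On the AE form and in section 8.1.5, record relatedness separately for Hexvix, for blue light/device, and for the procedure (catheterization, cystoscopy, biopsy/TURBT, anesthesia).
2. Redefine 'Uncertain' as a relationship that can be neither established nor excluded. Remove the timing condition and let the rival cause include the procedure. Leave the 'No' threshold as it is.
3. Report 'Yes' and 'Uncertain' separately as well as pooled. This matters more once 'Uncertain' is widened, because the pooled ADR rate may rise. State in section 10.4.3.1 how 'adverse reactions' differ from 'study drug-related adverse events'.
4. In section 10.4.3, tabulate AEs for randomized blue light, randomized white light only and training subjects, as well as pooled. Note that the white-light-only contrast is imprecise and does not inform on Hexvix itself.

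The cost is two more relatedness fields per AE, revised definitions and wider tables, with imprecise estimates in the small group.
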